1.1.2.2 Phase II

- To evaluate safety and tolerability of BMS-986253 with or without DNMTi in MDS participants, as well as clinical outcomes including overall improvement rate (OIR), transfusion-independence (TI), cytogenetic response rate, time to best response (CR, PR, marrow CR + HI, HI), disease free survival (DFS: definition: time to relapse for participants who achieve CR), progression-free survival (PFS; definition: disease progression or death from MDS), leukemia-free survival (LFS; definition: progression to AML or death from any cause), and overall survival (OS: definition: death from any cause).

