3.5.2 Efficacy Assessments

- Cytogenetic response rate
- Time to best response (CR, PR, marrow CR+HI, HI)
- Disease free survival (definition: time to relapse for participants who achieve CR)
- Progression free survival (definition: disease progression or death from MDS)
- Leukemia free survival (definition: progression to AML or death from any cause)
- Overall survival (definition: death from any cause)
- Transfusion-dependence and independence, for RBC and platelets

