Phase II: To evaluate safety and secondary clinical outcomes of BMS-986253 in MDS participants by cohort.	-Safety, as measured by: Incidence of AEs, SAEs; and AEs leading to discontinuation, death, and laboratory abnormalities, assessed from first cycle until time of disease relapse, disease progression, or death, whichever occurs first, assessed every 3-6 months - Clinical outcomes including: overall improvement rate (OIR), cytogenetic response rate, time to best response (CR, PR, marrow CR, or HI), disease free survival (DFS; definition: time to relapse for participants who achieve CR), progression free survival (PFS; definition: disease progression or death from MDS), leukemia free survival (LFS; definition: progression to AML or death from any cause), and overall survival (OS; definition:	Confirm safety and evaluate efficacy through long-term clinical outcomes

OBJECTIVES	ENDPOINTS	JUSTIFICATION FOR ENDPOINTS
	death from any cause); assessed every 3-6 months	
Exploratory		
To evaluate changes in serum cytokine levels pre- and post-treatment with BMS-986253.	Each of these will be evaluated using descriptive methods and reported as exploratory results. If any statistical tests are performed in these analyses, the results will be presented without adjustment for multiple comparisons but reported in the context of the number of tests performed. See section 5 for collection timepoints.	Evaluate mechanistic and immunologic effects of the study drug
To evaluate the cell composition in the peripheral blood and bone marrow microenvironment before and after treatment with BMS-986253.		
To evaluate changes in the transcriptome and proteome in response to treatment with BMS-986253.		
To determine the degree of bone marrow myeloid-derived suppressor cell (MDSC) infiltration.		
To describe changes in genetic clonal diversity during treatment with BMS-986253 in combination with DNMTi.		
To assess cell-autonomous effects on the MDS clone by measuring biomarkers in the Akt pathway (i.e. pS743) in MDS blasts.		
To evaluate cell-autonomous and microenvironment dependent activity of BMS-986253 using ex vivo culture of participant-derived		

OBJECTIVES	ENDPOINTS	JUSTIFICATION FOR ENDPOINTS
hematopoietic stem and progenitor cells.		
To assess quality of life improvement by participant reported outcomes using the EORTC QLQC30 score.		

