10.2 SAMPLE SIZE DETERMINATION

The trial will begin with a phase I dose escalation phase using a standard 3+3 design to determine OBD, separately for each cohort. With 3 dose levels per cohort (and dose level -1), and no more than 6 participants per dose level, up to 18 participants may be enrolled in phase I per cohort, total 36 maximum.

In phase I/II, there will be two cohorts:

1. “Higher-risk” MDS (HR-MDS) Cohort with R-IPSS ≥ 3.5 : Intermediate and high-risk participants receiving combination treatment
2. “Lower-risk” MDS (LR-MDS) Cohort with R-IPSS < 3.5 : Lower intermediate and low-risk participants receiving single agent anti-IL8 treatment.

Based on the literature, DNMTi previously untreated participants with intermediate and high-risk disease have clinical response rates of approximately 20-50%; thus, in view of heterogeneity of prior results a response rate of at least 40% in participants treated with combination therapy would be desirable. [75, 116] In participants with low-risk disease, response rates are likely to be lower, and expected to be less than 30% from monotherapy;[84, 91, 92] thus, also attaining a response rate of at least 30% with monotherapy would be considered desirable.

Participants enrolled during phase I who are treated at the OBD may be included in the first stage portion of the trial if they meet the same eligibility as the participants in the phase II portion.

The two phase II cohorts will each have their own sample size determination:

- In participants in the higher-risk HR-MDS cohort (with either intermediate or high-risk MDS), the trial will be conducted using a Simon optimal two-stage phase II trial design to rule out an unacceptably low response rate (CR+PR+mCR with HI) of 30% ($p_0=0.30$)

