in favor of an improved response rate of 50% ($p_1=0.50$) in order to determine if the combination will be able to potentially improve upon heterogeneous 20-50% response rates in participants who have received other agents. [75, 116] With $\alpha=0.10$ (probability of accepting a poor treatment=0.10) and $\beta=0.20$ (probability of rejecting a good treatment=0.20), the first stage will enroll 15 evaluable participants, including the 6 participants from the phase I dose escalation that reached OBD, and if 0 to 5 of the 15 has a response, then no further participants will be accrued. If 6 or more of the first 15 participants has a response, then accrual would continue until a total of 32 evaluable participants have been treated in that cohort. As it may take up to several months to determine if a participant has experienced a response, a temporary pause in the accrual may be necessary to ensure that enrollment to the second stage is warranted. If there are only 6-12 participants with a response out of 32 participants, this would be an uninterestingly low response rate. If there were 13 or more of 32 (40.6%) who experienced a response, treatment in this cohort would be sufficiently interesting to warrant further study in later trials. Under the null hypothesis (30% response rate), the probability of early termination is 72.2%.

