10.4.3 Analysis of the Secondary Endpoint(s)

- The secondary objectives for phase I are to describe pharmacokinetic properties of BMS-986253 in MDS participants and to evaluate safety and tolerability of BMS-986253 in MDS participants. The AUC, half-life, and Css of BMS-986253 will be evaluated in participants, separately by dose level and cohort using descriptive statistics.
- The secondary objectives for phase II are:
 - (a) to evaluate the safety and tolerability of the agent as measured by the grades and types of toxicity noted for the agent at each dose level, separately by cohort; and,
 - (b) to evaluate efficacy, as measured by clinical outcomes, including OIR (CR + PR + HI + marrow CR + SD), cytogenetic response rate, time to best response, disease free survival (DFS; definition: time to relapse for participants who achieve CR), progression free survival (PFS; definition: disease progression or death from MDS), leukemia free survival (LFS; definition: progression to AML or death from any cause), and overall survival (OS; definition: death from any cause).
 - OIR and cytogenetic response rate will each be reported as a fraction, separately by cohort, along with a 95% confidence interval. Time to best response, DFS,

PFS, LFS, and OS will be evaluated separately for each phase II cohort using the Kaplan-Meier method. In each case, the median time to event will be reported along with a 95% confidence interval for the median.

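### Time to best response is given a Kaplan-Meier median with no stated analysis set and no rule for leaving before response, and its response set differs between sections

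*Combined protocol and SAP*

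**What the plan says.** Section 10.4.3 lists time to best response and DFS at the start of a sentence that continues "PFS, LFS, and OS will be evaluated separately for each phase II cohort using the Kaplan-Meier method". It then adds "In each case, the median time to event will be reported along with a 95% confidence interval for the median". The same section defines DFS as "time to relapse for participants who achieve CR", so that endpoint has a restricted set. Time to best response has no such restriction. I found no rule for non-responders, for censoring, or for progression or death before response.

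The event is written in two ways:

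- Section 1.1.2.2: "time to best response (CR, PR, marrow CR + HI, HI". Section 3.5.2 agrees: "Time to best response (CR, PR, marrow CR+HI, HI". Here marrow CR counts only with HI.
- Section 10.1: "time to best response (CR, PR, marrow CR, or HI". Here marrow CR counts with or without HI.

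Section 10.4.3 names no set. Both versions include HI alone, so both are wider than the primary response in Section 10.2, which is CR, PR or marrow CR with HI.

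**The concern.** Response is a favourable event that many participants never have. Kaplan-Meier treats a censored participant as still able to have the event, at the same rate as those still followed. That does not fit someone who has progressed, died or stopped therapy without responding. Section 6.3 takes participants with progression off study, so censoring them would be the default coding if nothing else is specified.

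Three things are at stake. The promised median may not be estimable. A median may be reported when fewer than half of the cohort respond. And a participant with marrow CR but no HI is an event or a non-event depending on which section the programmer follows.

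**Working it through.** **1. The plan's own response-rate design.** Section 10.2 sets out Simon two-stage designs. For HR the aim is to "rule out an unacceptably low response rate (CR+PR+mCR with HI) of 30"% "in favor of an improved response rate of 50"%, stopping at 5 or fewer of 15 and succeeding at 13 or more of 32. For LR the rates are 20% and 40%, stopping at 2 or fewer of 12 and succeeding at 8 or more of 25. Early termination under the null is P(X ≤ r1), with X binomial(n1, p0):

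- HR: P(X ≤ 5 | 15, 0.30) = 72.16% (stated 72.2%); alpha 0.0997, power 0.804.
- LR: P(X ≤ 2 | 12, 0.20) = 55.83% (stated 55.8%); alpha 0.0991, power 0.815.

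The stated figures reproduce.

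**2. Can a whole-cohort median exist without early censoring?** The curve then levels off at 1 − responders/n. At the success thresholds this is 1 − 13/32 = 0.594 (HR) and 1 − 8/25 = 0.680 (LR). A cohort judged promising can therefore have no median on the ORR components. A median needs 16 of 32 (a curve that just touches 0.5 is counted as reached) or 13 of 25. Exact binomial tails:

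| Cohort | Rate | P(at least half respond) |
|---|---|---|
| HR, n=32 | 0.30 | 1.4% |
| HR, n=32 | 0.40 | 16.5% |
| HR, n=32 | 0.50 (target) | 57.0% |
| LR, n=25 | 0.20 | 0.04% |
| LR, n=25 | 0.30 | 1.8% |
| LR, n=25 | 0.40 (target) | 15.4% |

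Given that stage one is passed, the target-rate figures are 64.9% (HR) and 16.8% (LR).

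HI alone also counts here, so these are lower bounds. Its rate is not in the documents. If any-response rates are assumed to be 60% or 70% (HR), the chance is 90.8% or 99.5%. At 50% or 60% (LR) it is 50.0% or 84.6%.

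**3. What does censoring early leavers do?** The phase II response assessments after cycles 2 and 6 (study calendar, note r) fall at days 2 × 28 = 56 and 6 × 28 = 168. Assumptions that are not in the documents: a share w of responses falls at day 56 and the rest at day 168; a fraction e of the cohort leaves without response, evenly over days 28 to 168, and is censored. With true response fraction p:

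- Exits before day 56: e × 28/140 = 0.2e.
- S(56) = 1 − wp/(1 − 0.2e)
- S(168) = S(56) × [1 − (1 − w)p/(1 − e − wp)]

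For p = 0.40, w = 0.5, e = 0.30: S(56) = 1 − 0.20/0.94 = 0.787; S(168) = 0.787 × (1 − 0.20/0.50) = 0.472. So 1 − KM = 53%, and a median appears.

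For w = 0.75: S(56) = 1 − 0.30/0.94 = 0.681; S(168) = 0.681 × (1 − 0.10/0.40) = 0.511. So 1 − KM = 49%, and no median appears. For w = 1, 1 − KM = 0.40/0.94 = 43%.

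1 − KM at day 168 with w = 0.5:

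| True fraction | e = 0% | 20% | 27% | 30% |
|---|---|---|---|---|
| 30% | 30% | 35% | 38% | 39% |
| 40% | 40% | 47% | 51% | 53% |
| 45% | 45% | 53% | 58% | 60% |

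**4. Cross-check with other timing.** A simulation spread responses evenly over months 2 to 6 and censored 60% of non-responders early. A median appeared in 67% of LR runs at p = 0.40, against 15.4% without early censoring. For HR at p = 0.30 it appeared in 28% of runs, against 1.4%.

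**The case against.** A reader might infer that the median is bound to be either undefined or a product of censoring. The documents do not support that, for these reasons:

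- **Whole cohort is not written.** Evaluating by cohort does not say that every participant is in the risk set. The same sentence covers DFS, which is restricted to CR. A responders-only analysis is compatible with the text and would have a defined median. This stands, and it makes the missing analysis set the firm part of the point.
- **The ORR rates are a floor.** HI alone counts for this endpoint, and LR entry requires a cytopenia, so HI is directly relevant there. Even at the HR target of 50% the median is reached more often than not.
- **A false median needs particular timing and exits.** At a true 40% it does not appear when 75% or more of responses fall at day 56, even with 30% exits. With responses split evenly it needs exits above about 25% of the cohort.
- **Stopping at C7D1 is not the cause.** Those exits come after the cycle 6 assessment and correspond to the 0% column, where nothing is inflated.
- **A median not reached is a legitimate Kaplan-Meier result.** That is true, but it tells the reader little about how quickly responders respond.
- **Two response sets do not make a median undefined.** They make the event ambiguous, which is a separate fault. Appendix F records marrow CR with and without HI separately, so either version can be derived.
- **Little depends on the endpoint.** It carries no test or decision rule, Section 10.2 omits it from its list of secondary endpoints, and response fractions are reported alongside. This limits the severity.

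**Conclusion.** The point holds in a limited form. Section 10.4.3 prescribes a Kaplan-Meier median for time to best response without an analysis set and without a rule for progression, death or exit before response. On the natural whole-cohort reading, the median is reached with probability 57% (HR) and 15% (LR) at the target rates. Those figures use ORR components only, assume no early censoring, and are lower bounds. Censoring those who leave before the cycle 6 assessment pushes the curve above the true response fraction. Whether it crosses one half while under half respond depends on timing and exit rates that the documents do not give: 53% or 49% in the two worked cases at a true 40%.

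The conflict over marrow CR without HI is a plain contradiction between sections and rests on no assumption. Severity is low to moderate, because the endpoint is secondary and descriptive.

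**What to change.** - Use one response set in 1.1.2.2, 3.5.2, 10.1 and 10.4.3, and say explicitly whether marrow CR without HI counts.
- Take time to best response out of the Kaplan-Meier median sentence in 10.4.3. Report its median and range among responders, by cohort, beside the number of responders.
- If a whole-cohort curve is shown, use the cumulative incidence of response, with progression, death and end of treatment without response as competing events.

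The cost is a few lines of wording and minor programming. The sample size and decision rules do not change. The downside is that a responders-only summary is conditional on having responded, so it should not be compared between cohorts.

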10.4.4 Safety Analyses

The safety and tolerability of the agent will be evaluated by reporting the grades and types of toxicity noted for the agent at each dose level.

Our goal toxicity rate is less than 20% and toxicity assessment will use Bayesian toxicity monitoring with maximum probability of DLT of 0.2, prior distribution (1,1), maximum patients 32, minimum number of patients before stopping 6, cohort size 1, and posterior probability > 80%. Using this approach, the study would be paused for review for toxicities in 2/6, 3/7, or 4/11, 5/15, 6/20, 7/24, 8/28, or 9/32 patients. The same boundaries would apply to both the LR-MDS and HR-MDS cohorts up to their respective enrollment goals.

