≤ 1 out of 6 at highest dose level below the maximally administered dose that exhibits optimal biologic activity	This is the OBD and is generally the recommended phase 2 dose. At least 6 participants must be entered at the recommended phase 2 dose.

The report including the supporting safety data and delineation of each criteria met, with the dose-escalation decisions will be provided to the Sponsor ([contact]) before additional participants will be enrolled into the study. The Dose Escalation Determination form on the sponsor website: <https://nih.sharepoint.com/:u/r/sites/NCI-CCR-OCD-Communications/SitePages/Forms-and-Instructions.aspx?csf=1&web=1&e=uWBXtI> may be used for this purpose.

Documentation of dose escalation determinations including the criteria met must be provided to the Sponsor prior to dose administration at the next dose level. An OSRO Dose Escalation Determination template form is available for recording of dose escalation related PI determinations or another format may be used but all equivalent information and PI signature is required.

The completed form or equivalent documentation should be kept in the site study files, sent to the Sponsor and available for review by the OSRO Clinical Site Monitors.

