- In participants with low-risk MDS, the trial will be conducted using a Simon optimal two-stage phase II trial design to rule out an unacceptably low response rate (CR+PR+mCR with HI) of 20% ($p_0=0.20$) in favor of an improved response rate of 40% ($p_1=0.40$) in order to determine if monotherapy with BMS-986253 will be able to improve upon an expected response rate below 30% in participants who have received other agents. [76, 83, 84] With $\alpha=0.10$ (probability of accepting a poor treatment=0.10) and $\beta=0.20$ (probability of rejecting a good treatment=0.20), the first stage will enroll 12 evaluable participants, including the 6 participants from the phase I dose escalation, that reached MTD, and if 0 to 2 of the 12 has a response, then no further participants will be accrued. If 3 or more of the first 12 participants has a response, then accrual would continue until a total of 25 evaluable participants have been treated in that cohort. As it may take up to several months to determine if a participant has experienced a response, a temporary pause in the accrual may be necessary to ensure that enrollment to the second stage is warranted. If there are only 3-7 participants with a response out of 25 participants, this would be an uninterestingly low response rate. If there were 8 or more of 25 (32.0%) who experienced a response, treatment in the appropriate cohort would be sufficiently interesting to warrant further study in later trials. Under the null hypothesis (20% response rate), the probability of early termination is 55.8%.

Secondary endpoints include progression free survival, overall survival, median survival, duration of response, and leukemia free survival. These will be determined separately in each of the phase II cohorts. Overall survival is considered an important endpoint in these participants and will be considered the most important secondary endpoint.

It is expected that up to 12-15 participants with MDS may be accrued per year. Thus, in order to accrue up to $18+18+32+25 = 93$ participants, it is expected that 4-5 years may be required to accrue the total number of required evaluable participants. In order to allow for a small number of inevaluable participants and potentially large number of screen failures, the accrual ceiling will be set at 200 participants.

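### Under the six-participant minimum, a pause already made certain by two early toxicities waits for up to four more participants; pausing at the second toxicity within the first six leaves the overall pause probability unchanged

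*Combined protocol and SAP*

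**What the plan says.** Section 10.4.4 (Safety Analyses) defines a Bayesian rule for each cohort whose ceiling, prior and maximum size are given as "maximum probability of DLT of 0.2, prior distribution (1,1), maximum patients 32". The timing of the looks is fixed by "minimum number of patients before stopping 6, cohort size 1", while the threshold is written as "posterior probability > 80" per cent. From this it concludes that "the study would be paused for review for toxicities in 2/6, 3/7, or 4/11, 5/15, 6/20, 7/24, 8/28, or 9/32 patients". On scope it adds: "The same boundaries would apply to both the LR-MDS and HR-MDS cohorts up to their respective enrollment goals". The goals are 32 (HR-MDS) and 25 (LR-MDS).

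Section 10.2 brings phase I participants into the first stage of each phase II cohort. For HR-MDS, "the first stage will enroll 15 evaluable participants, including the 6 participants from the phase I dose escalation that reached OBD"; for LR-MDS the twelve are described as "including the 6 participants from the phase I dose escalation, that reached MTD". The same section also makes this inclusion optional and subject to phase II eligibility. Section 10.4.4 does not say whether these participants count toward the toxicity boundaries.

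The decision table in section 3.1.2 stops escalation at two or more DLTs at a dose level, without waiting for six participants. It accepts the OBD only with at most 1 DLT in 6, and states: "At least 6 participants must be entered at the recommended phase 2 dose".

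**The concern.** The rule looks after every participant but cannot act until the sixth. Two toxicities in two, three, four or five participants are stronger evidence against the 20% ceiling than two in six, yet only two in six triggers the pause. Once the second toxicity has occurred, the outcome at the sixth participant is settled, whatever happens to those in between. They are exposed while a review that is bound to happen is held back. The plan's phase I rule does not wait in this way.

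**Working it through.** **Inputs.** All are from section 10.4.4: prior Beta(1,1), ceiling 0.20, posterior threshold 0.80, minimum 6, a look after each participant, maximum 32 (25 for LR-MDS, from section 10.2).

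**Step 1. Reproduce the plan's boundaries.** After x toxicities in n participants the posterior is Beta(1+x, 1+n−x). The rule pauses when P(rate > 0.20) > 0.80. For whole numbers this probability equals P(Y ≤ x), where Y is binomial with n+1 trials and probability 0.20.
- 2/6 gives 0.852, so it pauses. 2/7 gives 0.797, so three are needed at n = 7.
- 3/11 gives 0.795, so four are needed. 8/32 gives 0.79996, just short, so nine are needed.

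All eight listed boundaries reproduce when each is read as the point where the required count steps up: 2 at n = 6, 3 at 7–10, 4 at 11–14, 5 at 15–19, 6 at 20–23, 7 at 24–27, 8 at 28–31 and 9 at 32.

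**Step 2. Apply the same criterion before six.**

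| n | 1 toxicity | 2 toxicities |
|---|---|---|
| 1 | 0.960 | – |
| 2 | 0.896 | 0.992 |
| 3 | 0.819 | 0.973 |
| 4 | 0.737 | 0.942 |
| 5 | 0.655 | 0.901 |
| 6 | 0.577 | 0.852 |

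Two toxicities exceed 0.80 at every n from 2 to 6. Since the count cannot decrease, two by n = 5 means at least two at n = 6, so the pause is certain. One toxicity exceeds 0.80 only at n = 1 to 3 and does not trigger at six.

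**Step 3. How often this happens, and what it costs.** With true rate p, the second toxicity falls on participant k with probability (k−1)p²(1−p)^(k−2). At p = 0.20 this is 0.0400, 0.0640, 0.0768, 0.0819 and 0.0819 for k = 2 to 6.
- The sum is 0.345, the chance of a pause at six. The part with k ≤ 5 is 0.263.
- Each such path enrols 6−k participants after the second toxicity. The average over all paths is 4(0.0400) + 3(0.0640) + 2(0.0768) + 1(0.0819) = 0.588. Given a pause at six it is 0.588/0.345 = 1.7.

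| True rate | Second toxicity by participant 5 | Pause at six | Mean spared, given that pause | Mean spared, overall |
|---|---|---|---|---|
| 10% | 8.2% | 11.4% | 1.5 | 0.17 |
| 20% | 26.3% | 34.5% | 1.7 | 0.59 |
| 30% | 47.2% | 58.0% | 1.9 | 1.13 |
| 40% | 66.3% | 76.7% | 2.2 | 1.70 |

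**Step 4. Full operating characteristics.** These come from exact recursion over binomial paths, assuming each outcome is known before the next look. Expected enrolment counts participants up to the pause, or to the maximum if there is none. The amended rule pauses at the second toxicity within the first six, then uses the listed boundaries.

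| True rate | Overall pause probability, both rules (N = 32) | Expected enrolment, plan → amended (N = 32) | Expected enrolment, plan → amended (N = 25) |
|---|---|---|---|
| 20% | 56.5% | 19.4 → 18.9 | 16.3 → 15.7 |
| 30% | 89.1% | 11.7 → 10.6 | 10.9 → 9.7 |
| 40% | 98.8% | 8.0 → 6.3 | 7.8 → 6.1 |

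At a true 10% the overall pause probability is 15.4% under both rules with N = 32.

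**The case against.** **The minimum is not idle.** A reader might infer that it only delays pauses and could be deleted. The plan's own criterion does not support that. Without a minimum, 1/1, 1/2 and 1/3 would also pause, and the overall pause probability (N = 32) would rise from 15.4% to 31.5% at a true 10% and from 56.5% to 67.7% at 20%. This objection stands. It limits the point to the two-toxicity paths and is why single-toxicity protection should be kept.

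**The delay may never arise.** If the six phase I participants at the OBD fill the first six places, the 3+3 rule has already held them to at most 1 of 6 first-cycle DLTs. This also stands: in that case the amendment delays nothing and costs nothing. A reader might go further and infer that 2/6 could then never be reached. That is too strong, because the phase I limit concerns one 28-day cycle, while section 10.4.4 speaks of toxicities without a time window. Nor is carry-over assured: HR-MDS phase I admits up to 8 prior DNMTi cycles and phase II only 4, so some may not qualify.

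**Extra exposure and dilution cannot be added together.** One might argue both that new participants wait for a pause and that a group selected for low toxicity dilutes the count. The first requires that the phase I six are not counted, the second that they are.

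**Other safeguards exist.** The team discusses each participant weekly (section 7.4.1), the study may be suspended for unacceptable risk (section 13.1), and the boundary triggers only a review. So it would be wrong to say that the trial cannot react before six. These safeguards are discretionary, however, and do not explain why the prespecified trigger should wait.

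**Conclusion.** The point holds in this limited form. On paths with two toxicities among the first two to five counted participants, waiting for the sixth changes no decision and adds between one and four exposed participants. Given a pause at six, an average of 1.5 to 2.2 would be spared across true rates of 10% to 40%. The effect on expected enrolment is modest at 20% (about 0.6) and larger at 40% (1.7). It rests on two assumptions: that the first six counted are new phase II participants, and that outcomes are known as each participant is assessed.

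Who counts is a separate, open question, and the answer is not neutral. Over 26 new HR-MDS participants (32 − 6), the pause probability at a true 10% is 15.3% if counting starts afresh, against 1.4% with 0/6 carried in and 9.1% with 1/6. At a true 30% the figures are 86.5%, 59% and 80%. Starting the count afresh detects excess toxicity more often but also pauses an acceptable dose more often, and it sets aside data from the same dose. The documents do not settle that trade-off, so it is for the sponsor.

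**What to change.** In section 10.4.4, keep the provision that one toxicity does not trigger a pause before six participants. Add that the cohort is paused for review as soon as a second toxicity occurs within the first six (2/2, 2/3, 2/4, 2/5 or 2/6), and that the listed boundaries apply from then on. This takes one sentence, needs no new data or additional looks, and leaves the overall pause probability unchanged in both cohorts.

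Separately, state whether phase I participants carried into the first stage count toward the boundaries, and reconcile this with section 10.2, which treats their inclusion as settled in one place and optional in another. That choice does change the pause probability, so the sponsor should report the operating characteristics for the option chosen.
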